### 7.7.4 Vital Signs

The following vital signs and  $SpO_2$  at room air (%) by pulse oximetry will be listed and summarized by treatment group and visit.

- systolic and diastolic blood pressure (mmHg);
- pulse rate (beats/min);
- temperature (°C);
- respiration rate (breaths/min).

Vital signs and SpO2 at room air (%) data and their changes from baseline will be summarized by visit using standard descriptive statistics by treatment group and overall plitidepsin for the As Treated population. The baseline value will be defined as last scheduled or unscheduled non-missing value collected prior to the first dose of the first study drug administration. Assessments carried out on day of first study drug administration are considered to have taken place before the study drug administration, if the corresponding times have not been recorded. For postbaseline, only data from scheduled visits will be included in the summary tables

If more than 10% of the patients preform an unscheduled vital signs assessment at the same relative day to the start date of study treatment then the vital signs and  $SpO_2$  at room air data will be also summarised at the specific relative day. In case of several unscheduled vital signs and  $SpO_2$  at room air assessments at the same day we will use the worst result.

For the above summaries, the vital signs and SpO2 at room air (%) assessed just before the start and immediately at the end of the plitidepsin infusion (for patients randomised to plitidepsin arms) will not be taken into account. These assessments will be summarized separately, the vital signs and SpO2 at room air (%) assessed just before the start and immediately at the end of the plitidepsin infusion; and the change from the start to the end of the plitidepsin infusion (end of the plitidepsin infusion value – start of the plitidepsin infusion value) will be summarized by visit for the plitidepsin arms and overall plitidepsin using standard descriptive statistics for the As Treated population.

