### Table 14.1.2.1.5 Post-hoc Analysis: Summary of Demographic Characteristics - All Patients Except Those from Site ES40 (Intent-To-Treat Population)

#### Table 14.1.3.1.1 Post-hoc Analysis: Summary of Baseline Characteristics (Intent-To-Treat Population)

Characteristic Statistic	Plitidepsin 2.5mg (N=XXX)	Plitidepsin 1.5mg (N=XXX)	Control Arm (N=XXX)	Total (N=XXX)
Chest Imaging at Enrolment, n (%)				
Pulmonary Infiltrates	xxx (xxx.x)	xxx (xxx.x)	xxx (xxx.x)	xxx (xxx.x)
Pleural Fluid	xxx (xxx.x)	xxx (xxx.x)	xxx (xxx.x)	xxx (xxx.x)
Atelectasis	xxx (xxx.x)	xxx (xxx.x)	xxx (xxx.x)	xxx (xxx.x)
Pulmonary Oedema	xxx (xxx.x)	xxx (xxx.x)	xxx (xxx.x)	xxx (xxx.x)
Bilateral Pneumonia	xxx (xxx.x)	xxx (xxx.x)	xxx (xxx.x)	xxx (xxx.x)
Lateral Pneumonia	xxx (xxx.x)	xxx (xxx.x)	xxx (xxx.x)	xxx (xxx.x)
Other	xxx (xxx.x)	xxx (xxx.x)	xxx (xxx.x)	xxx (xxx.x)
Periods of inclusion, n (%)				
Beginning of accrual - August 2021	xxx (xxx.x)	xxx (xxx.x)	xxx (xxx.x)	xxx (xxx.x)
September 2021 - March 2022	xxx (xxx.x)	xxx (xxx.x)	xxx (xxx.x)	xxx (xxx.x)
April 2022 - End of accrual	xxx (xxx.x)	xxx (xxx.x)	xxx (xxx.x)	xxx (xxx.x)

<continue for the following characteristics: Systolic Blood Pressure (mmHg) at Screening, Diastolic Blood Pressure (mmHg) at Screening, pulse rate (beats/min) at Screening, temperature (C) at Screening, respiration rate (breaths/min) at Screening, oxygen saturation at room air (%) at Screening and FiO2 (%) at Screening>

Vaccination Status, n (%)				
Fully Vaccinated	xxx (xxx.x)	xxx (xxx.x)	xxx (xxx.x)	xxx (xxx.x)
Non-Fully Vaccinated	xxx (xxx.x)	xxx (xxx.x)	xxx (xxx.x)	xxx (xxx.x)
No Vaccinated	xxx (xxx.x)	xxx (xxx.x)	xxx (xxx.x)	xxx (xxx.x)
Fully Vaccinated+ Non-Fully	xxx (xxx.x)	xxx (xxx.x)	xxx (xxx.x)	xxx (xxx.x)
Vaccinated				

N = number of patients in analysis set; n = number of patients with data available; % = percentages are calculated based on N as the denominator. SD = Standard deviation; Q1 =25th percentile; Q3 = 75th percentile; Min = Minimum; Max = Maximum. Reference: Listing 16.2.4.2

Programming notes (not part of the table):

- Table template TDM002.
- Include all parameters detailed in Table 14.1.3.1.
- The displayed xxx do not reflect actual decimal precision. Please follow Section 2.11 for rounding rules.

• A "Missing" category should only be presented under the subcategories for any categorical variable in case of missing data.

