Note: "at room air" have been removed from 'Oxygen saturation" label as it is not applicable in Tables 14.1.3.1, 14.3.5.1, 14.3.5.2 and Listing 16.2.4.2.

The below tables are a repeat of table 14.1.3.1.1 Post-hoc:

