## 2.2 Overall Study Design

This is a randomised, multicentre, open-label, controlled Phase 3 study in which adults requiring hospital admission and oxygen supplementation for management of moderate COVID-19 infection will be randomised in 1:1:1 to:

- Plitidepsin 1.5 mg arm: Patients will receive plitidepsin 1.5 mg/day intravenous (IV) in addition to dexamethasone on days 1 to 3;
- Plitidepsin 2.5 mg arm: Patients will receive plitidepsin 2.5 mg/day IV in addition to dexamethasone on days 1 to 3;
- Control arm: Patients will receive dexamethasone IV on Days 1 to 3. Additionally, in accordance with local treatment guidelines, patients in this group may receive a regulatory-approved antiviral treatment.

The study allows up to a total cumulative dose of 60 mg of dexamethasone base (calculation of the total dose will also include corticosteroids administered within 72 hours before the start of the study treatment and dexamethasone administered as premedication).

Randomisation will be stratified for 3 factors:

- Geographical region (Europe vs. Rest of the World);
- Charlson Comorbidity Index (0-1 vs. >1); and
- Barthel Index (≥90 versus <90)

From treatment initiation on Day 1, patients will be followed in the hospital for at least 4 days and then through Day 31 ( $\pm$ 3 days) or resolution/stabilisation of treatment-related adverse events (AEs), treatment-emergent adverse events (TEAEs) of special interest, and serious adverse events (SAEs). Patients discharged from the hospital prior to Day 8 will return to an out-patient clinic for assessments on Days 8 ( $\pm$ 1 day), and 31 ( $\pm$ 3 days). On Day 15 ( $\pm$ 1 day), patients will be followed up in remote or on-site visit (Appendix 4).

An independent Data Monitoring Committee (IDMC) will oversee study conduct (safety and primary endpoint), including analysis of summary safety data as per the trial requirements.

The study is expected to randomise approximately 609 patients (203 in each arm) over a period of 20 months.

Patients will be considered to be on study from the signature of the informed consent form until the end of the follow-up period, that is, completion of the protocol-specified follow-up visit on Day 31 ( $\pm$ 3 days) or until resolution/ stabilisation of treatment-related AEs, TEAEs of special interest, and SAEs that occurred through Day 31, whichever is longer.

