#### CONFIDENTIAL

\*Body weight and height should be measured at screening.

- 1 Informed consent: Must be obtained before the patient undergoes any study-specific procedure
- 2 Selection criteria: Confirm that patient meets all inclusion criteria and none of the exclusion criteria
- 3 Vital signs: Temperature, sitting blood pressure, heart rate, respiratory rate, PaO2 (obtained either by arterial blood gas analyses or from saturation of oxygen (SpO2) by pulse oximetry, and its respective FiO2 to be measured at screening, on Days 1 to 3 just before start and end of each plitidepsin infusion (plitidepsin groups)/once daily on Days 1 to 3 (control group), further once daily while the patient is hospitalised, and on Days 8, and 31 (±3 days). To estimate the PaO2/FiO2 ratio, the required equation would be used for imputing PaO2 from SpO2, and the information on the oxygen delivery devices and oxygen flow prescribed would be utilised for imputation of FiO2.
- 4 ECG: QTcF prolongation to be assessed at screening and on Days 1, 3 (postinfusion), and 31 (±3 days), and any QTcF values >500 msec will be flagged as increasing the likelihood of the treatment being proarrhythmic (per ICH Guidance E14)
- 5 Haematology: RBC, haemoglobin, haematocrit, WBC with differential, platelet count. Testing to be performed by the local laboratory for screening and by central laboratory for on-study tests (tests performed within 24 hours of screening do not have to be repeated)

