# 3.14 Vital Signs

#### Table 14.3.5.1 Summary of Vital Signs and Oxygen Saturation - Change from Baseline (As Treated Population)

Parameter (unit)									
	Plitidepsin 2.5mg (N=XXX)		Plitideps (N=Y	sin 1.5mg XXX)	Plitidep (N=2	psin Total Contro =XXX) (N=X		ol Arm KXX)	
Visit Statistic	Value at Visit	Change from Baseline	Value at Visit	Change from Baseline	Value at Visit	Change from Baseline	Value at Visit	Change from Baseline	
Baseline									
n Mean (SD) Median Q1, Q3 Min, Max	xxx xx.xx (xx.xxx) xx.xx xx.xx, xx.xx xx.x, xx.xx		XXX XX.XX (XX.XXX) XX.XX XX.XX, XX.XX XX.X, XX.X		XXX XX.XX (XX.XXX) XX.XX XX.XX, XX.XX XX.X, XX.X		XXX XX.XX (XX.XXX) XX.XX XX.XX, XX.XX XX.X, XX.X		
Day 2 – Pre-Infusion									
N Mean (SD) Median Q1, Q3 Min, Max	XXX XX.XX (XX.XXX) XX.XX XX.XX, XX.XX XX.X, XX.X	XXX XX.XX (XX.XXX) XX.XX XX.XX, XX.XX XX.X, XX.X	xxx xx.xx (xx.xxx) xx.xx xx.xx, xx.xx xx.x, xx.x	xxx xx.xx (xx.xxx) xx.xx xx.xx, xx.xx xx.x, xx.x	XXX XX.XX (XX.XXX) XX.XX XX.XX, XX.XX XX.X, XX.X	xxx xx.xx (xx.xxx) xx.xx xx.xx, xx.xx xx.x, xx.x	NA	NA	
Day 2 n Mean (SD) Median Q1, Q3 Min, Max etc.	NA	NA	NA	NA	NA	NA	xxx xx.xx (xx.xxx) xx.xx xx.xx xx.xx, xx.xx xx.x, xx.x	XXX XX.XX (XX.XXX) XX.XX XX.XX, XX.XX XX.X, XX.X	

N = number of patients in analysis set; n = number of patients with data available.

SD = Standard deviation; Q1 = 25th percentile; Q3 = 75th percentile; Min = Minimum; Max = Maximum; NA= Not Applicable.

Notes: The baseline value is defined as last scheduled or unscheduled non-missing value collected prior to the first dose of the first study drug administration. Reference: Listing 16.2.8.2.1

- Table template TVS002B.
- Parameters are: Systolic Blood Pressure (mmHg); Diastolic Blood Pressure (mmHg), Pulse rate (beats/min); Temperature (°C); Respiration Rate (breaths/min) and Oxygen Saturation at Room Air (%).
- Visits: Day 2 Pre-Infusion, Day 2, Day 3 Pre-Infusion, Day 3, Day 4, Day 5, Day 6, Day 7, Day 8, and Day 31.

• The displayed xxx do not reflect actual decimal precision. Please follow Section 2.11 for rounding rules.

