#### Listing 16.2.6.4 Oxygen status (Intent-To-Treat Population)

Treatment Group: << Plitidepsin 2.5mg/Plitidepsin 1.5mg/Control Arm>>

Site ID - Patient ID	Age/Sex/Race [a]	Altitude (m)	Date/Time of Assessment/ Change (Day) [b]	Oxygen Status	SpO2 (%)	FiO2 (%)	PaO2 (mmHg)	PaO2/FiO2 adjusted by Altitude
XXXX-YYYYY	XX/X/X	XXXX	DDMMMYYYY/HH:MM (XX)	xxxxxxxxxxxxx	XXXX	xxxx	xxxx	XXXX
123-456789	45/M/W	759	02MAR2018/12:30 (1) 06MAR2018/12:30 (5) 11MAR2018/12:30 (10)	High flow oxygen Low flow oxygen No supplemental oxygen needed	93.5 95.7 98.1	40 45 50	67 85 98	167.5 188.9 196.0
etc.				heeded				

[a] For sex, F = Female; M = Male. For race, AI = American Indian or Alaska native; A = Asian; BA = Black or African American; PI = Native Hawaiian or Other Pacific Islander; W = White; O = Other; UN = Unknown.
[b] Relative to the start of study treatment.

- Listing template LEF001.
- Order by Site ID Patient ID and Date/Time of Assessment/ Change.

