### Listing 16.2.8.2.1 Vital Signs and Oxygen Saturation (As Treated Population)

Treatment Group: << Plitidepsin 2.5mg/Plitidepsin 1.5mg/Control Arm>>

Site ID - Patient ID	Age/Sex/Race [a]	Parameter (unit)	Visit	Date/Time of Collection (Day) [b]	Value*	Change from Baseline	Change from Start Infusion
XXXX-YYYYY	XX/X/X	XXXXXXXXXX (XXXX)	XXXXXXXXX	DDMMMYYYY /HH:MM (XX)	XXXX	XXXX	
123-456789	45/M/W	SBP (mmHg)	Screening Day 1	19JAN2018 (-1) 20JAN2018 (1)	132 139		
			Day 1 – Start Infusion	20JAN2018/09:30 (1)	136*		
			Day 1 – End of Infusion	20JAN2018/11:05 (1)	140		4
			Day 2	21JAN2018 (2)	140	4	
			Day 2 – Start Infusion	21JAN2018/09:30 (2)	138	2	
			Day 2 – End of Infusion	21JAN2018/11:05 (2)	136		-2
			Day 3	22JAN2018 (3)	114	-22	
			Day 3 – Start Infusion	22JAN2018/09:30 (3)	116	-20	
			Day 3 – End of Infusion	22JAN2018/11:05 (3)	112		-4
			Day 4	23JAN2018 (4)	114	-22	
etc.			-				

Notes: The baseline value is defined as last scheduled or unscheduled non-missing value collected prior to the first dose of the first study drug administration.

\* Baseline value; Start Infusion = Just before the start of the plitidepsin infusion; After Infusion = Immediately at the end of the plitidepsin infusion.

[a] For sex, F = Female; M = Male. For race, AI = American Indian or Alaska native; A = Asian; BA = Black or African American; PI = Native Hawaiian or Other Pacific Islander; W = White; O = Other; UN = Unknown.

[b] Relative to the start of study treatment.

- Listing template LVS001A.
- Parameters are: Systolic Blood Pressure (mmHg); Diastolic Blood Pressure (mmHg), Pulse rate (beats/min); Temperature (°C); Respiration Rate (breaths/min), SpO2 (%), FiO2 (%) and PaO2 (mmHg).
- Include all Visits available in data including any unscheduled Visits.
- Order by Site ID Patient ID, parameter and Visit.

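### Change in SpO2 is summarised without the FiO2 at which it was measured, so worsening can be hidden or understated, and the room-air label is only partly withdrawn

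*SAP*

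**What the plan says.** Section 7.7.4 names SpO2 at room air alongside the vital signs and says that these "data and their changes from baseline will be summarized by visit using standard descriptive statistics by treatment group and overall plitidepsin". It also plans a separate summary of the change from start to end of each plitidepsin infusion. The version 4.0 shell for Table 14.3.5.1 repeats the label in its parameter list, "Respiration Rate (breaths/min) and Oxygen Saturation at Room Air", and the shell for Table 14.3.5.2 (infusion change) does the same. Neither shell includes FiO2 or an oxygenation ratio.

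Section 2.2 describes the population as "adults requiring hospital admission and oxygen supplementation for management of moderate COVID-19 infection". Appendix 4, footnote 3, pairs SpO2 with its corresponding FiO2 at screening, around each infusion on Days 1 to 3, daily in hospital and at follow-up, and adds that "the information on the oxygen delivery devices and oxygen flow prescribed would be utilised for imputation of FiO2".

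The SAP addendum (version 2.0, 12 September 2023) carries a note under Table 14.1.3.1.1 that takes the room-air words out of the oxygen-saturation "label as it is not applicable in Tables 14.1.3.1, 14.3.5.1, 14.3.5.2 and Listing 16.2.4.2". The shell of Table 14.1.3.1.1 itself still reads "oxygen saturation at room air (%) at Screening and FiO2 (%) at Screening".

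After Screening, FiO2 appears by patient in Listing 16.2.8.2.1 ("Respiration Rate (breaths/min), SpO2 (%), FiO2 (%) and PaO2 (mmHg") and in Listing 16.2.6.4, which also holds "PaO2/FiO2 adjusted by Altitude". No table summarises either quantity after Screening.

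**The concern.** An SpO2 value can be read only together with the oxygen being delivered. If the two readings being subtracted were taken at different FiO2, their difference mixes a change in the patient's gas exchange with a change in treatment. A patient who deteriorates and is given more oxygen may show little or no change, and one who recovers and is weaned may show a fall. Averaged over an arm, the table could reassure when it should not, or the reverse.

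The issue bears on the safety objective about variations of vital signs (Section 2.1.3.2) and on the infusion table, in a trial that premedicates against infusion reactions and counts falls in oxygen saturation and hypoxia among its adverse events of special interest (Section 7.7.2). Removing a label does not alter what is averaged and subtracted.

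**Working it through.** The plan gives no figure on this point to reproduce. The check is a comparison of passages, followed by an illustration.

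**Step 1: what is measured against what is summarised.**
- Population (Section 2.2): on supplementary oxygen at entry, so a room-air baseline is not to be expected.
- Measurement (Appendix 4, footnote 3): SpO2 with its FiO2, the latter imputed from device and flow. Readings are therefore taken on delivered oxygen.
- Summary (Section 7.7.4 and the two shells): SpO2 at room air, with change, and no condition on FiO2.
- Correction (addendum note): the label goes from Tables 14.1.3.1, 14.3.5.1 and 14.3.5.2 and Listing 16.2.4.2. The quantity analysed stays the same. FiO2 is added to one table, at Screening only.

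**Step 2: what the planned change can show.** The planned quantity is later SpO2 minus starting SpO2. The comparison quantity is SpO2 (%) divided by FiO2 (as a fraction). All values below are assumed; none comes from the SAP.

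| Assumed course | Start: SpO2, FiO2 | Later: SpO2, FiO2 | Planned change | SpO2/FiO2 |
|---|---|---|---|---|
| Worse, SpO2 held | 95%, 0.28 | 95%, 0.40 | 0 | 95/0.28 = 339 to 95/0.40 = 238 (-30%) |
| Worse, SpO2 held | 95%, 0.28 | 95%, 0.50 | 0 | 339 to 95/0.50 = 190 (-44%) |
| Worse, SpO2 partly held | 94%, 0.28 | 90%, 0.60 | -4 points | 94/0.28 = 336 to 90/0.60 = 150 (-55%) |
| Recovering, weaned to air | 95%, 0.50 | 92%, 0.21 | -3 points | 190 to 92/0.21 = 438 (+131%) |

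The first two rows are flat, the third is attenuated, and the fourth has the wrong sign. When SpO2 is constant, the relative fall in the ratio is 1 - (starting FiO2/later FiO2), for example 1 - 0.28/0.50 = 0.44. It depends only on the FiO2 values chosen, so it shows direction and not frequency.

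**Step 3: the oxygen mix shifts over the visits.** Section 2.3 assumes a median time to sustained oxygen withdrawal of 8 days (control) and 5.7 days (plitidepsin), with 530 events in 609 patients, and 530/609 = 87%. On those assumptions baseline readings are mostly on oxygen, Day 8 readings are mixed, and Day 31 readings are mostly on air. The change from baseline thus compares different oxygen conditions by design. These are design expectations; recruitment stopped early (Section 8).

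**Step 4: what other outputs add.** The WHO scale and the oxygen, high-flow and ventilation endpoints classify patients by type of support, by day or by period. They do not show a rise in FiO2 within one type of support, nor a change during a 60-minute infusion. Table 14.3.5.2 is the planned summary of saturation for that interval.

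**The case against.** The strongest reply is that respiratory worsening is already well covered. The primary endpoint is withdrawal of oxygen. WHO status, oxygen therapy, high-flow oxygen, non-invasive and invasive ventilation, time to intensification, duration of advanced support and ICU admission are all summarised by arm. Adverse events of special interest include desaturation, hypoxia and acute respiratory failure, respiration rate stands in the same two tables, and interrupted infusions are counted. The SpO2 table is descriptive, carries no test and changes no efficacy result. The addendum has already dropped the label from the two tables at issue. All of this stands, and it limits the weight of the point. It does not close the two gaps in Step 4.

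A reader might infer more than the document supports:
- *That the SpO2 change must stay flat, or that the table cannot show a difference between arms.* The SAP states no saturation target and gives no data; the third row of the illustration moves by 4 points. Only the possibility is established.
- *That FiO2 is merely listed.* The addendum summarises it at Screening; only later values are confined to listings.
- *That room-air readings hardly exist.* That is likely at baseline, but the design expects most patients to be off oxygen by the end of follow-up.
- *That the vital-signs objective goes unanswered.* The other vital signs are summarised as planned, and oxygen need is compared elsewhere.

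**Conclusion.** The point holds within limits. Section 7.7.4 and the version 4.0 shells describe a room-air measurement that the schedule does not collect as such. The addendum corrects this in part and leaves its own baseline shell in conflict with its own note. Raw SpO2 at differing FiO2 is still averaged and subtracted, so the by-visit and infusion changes can be flat, attenuated or reversed relative to the patient's course.

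The conclusion assumes that SpO2 is read on delivered oxygen, as footnote 3 implies, and that FiO2 differs between the compared time points in some patients. How many cannot be derived from the document. The effect is confined to descriptive As Treated safety tables; the primary and key secondary analyses are unaffected. The change is worth making because it is cheap and because nothing else planned summarises oxygenation across an infusion or within one type of support.

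**What to change.** 1. Remove the room-air wording from Section 7.7.4 and from the addendum shell for Table 14.1.3.1.1, so that both agree with the addendum note and with footnote 3. The same wording in the list of screening variables in Section 7.4 should go with it.
2. In Tables 14.3.5.1 and 14.3.5.2, keep the raw SpO2 row and add rows for FiO2 and SpO2/FiO2, setting FiO2 to 0.21 when no supplemental oxygen is recorded. Give value and change from baseline by arm in the first table, and value and change from start to end of infusion by plitidepsin arm in the second.
3. A by-visit summary of PaO2/FiO2 is optional.

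The cost is derivation and programming only, since the variables are already in Listings 16.2.6.4 and 16.2.8.2.1 and no new assessment is needed. The database was locked on 26 April 2023, so the added rows should be marked post hoc, like the addendum's other outputs. The limitation to state in a footnote is that FiO2 is imputed from device and flow, which makes the ratio approximate. PaO2 may itself be imputed from SpO2, so PaO2/FiO2 may have both terms imputed.

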# 7.7.5 Electrocardiograms

The following quantitative ECG measurements will be taken in triplicates during the study:

- heart rate (beats/min);
- RR interval (msec);
- PR interval (msec);
- QRS interval (msec);
- QT interval (msec);
- Fridericia corrected QT (QTcF) interval (msec);

The average QTcF interval (msec) values and changes from baseline will be summarized by treatment group and overall plitidepsin, and by visit using standard descriptive statistics for the As Treated population.

The Baseline value will be defined as last scheduled or unscheduled non-missing value collected prior to the first dose of the first study drug administration. Assessments carried out on day of first study drug administration are considered to have taken place before the study drug administration, if the corresponding times have not been recorded. For post-baseline, only data from scheduled visits will be included in the summary tables.

In addition, the number and percentage of patients with a potentially clinically important ECG result defined as:

- Average QTcF interval value > 500 msec
- Change from baseline in QTcF interval > 30 msec

will be tabulated by treatment group and overall plitidepsin, and visit for the As Treated population.

Patients participating in the QTc substudy will have additional measurements by continuous 12-lead ECG automated monitoring over Days 1 to 3. The QTc substudy will be managed by a vendor (ERT - eResearchTechnology, Inc). The data analysis methods will be detailed in a separate statistical analysis plan and results will be reported separately.

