#### 2.1.3.2 Safety Secondary Objectives

The safety secondary objectives of this study are

- To compare safety/tolerability of plitidepsin 1.5 mg or 2.5 mg versus the control in terms of adverse events, adverse reactions and mortality.
- To compare safety/tolerability of plitidepsin 1.5 mg or 2.5 mg versus the control in terms of abnormal laboratory parameters.
- To compare safety/tolerability of plitidepsin 1.5 mg or 2.5 mg versus the control in terms of variations of vital signs.

• To compare safety/tolerability of plitidepsin 1.5 mg or 2.5 mg versus the control in terms of ECG variations.

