## 3.4 Safety Variables

The safety/tolerability endpoints are as follows:

- Frequency of TEAEs, TEAEs ≥ grade 3 according to the National Cancer Institute-Common Terminology Criteria for AEs (NCI-CTCAE, version 5.0), TEAEs of special interest, serious TEAEs, serious treatment-related TEAEs, TEAEs leading to treatment discontinuation, and deaths.
- Actual and change from Baseline in clinical laboratory results.
- Actual and change from Baseline in vital signs results.
- Actual and change from Baseline in ECG findings.

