### 3.15 Electrocardiograms (ECGs)

#### Table 14.3.6.1 Summary of 12-Lead Electrocardiogram (ECG) Parameters - Change from Baseline (As Treated Population)

Parameter (unit)								
	Plitidepsin 2.5mg (N=XXX)		Plitideps (N=X	sin 1.5mg XXX)	Plitidepsin Total (N=XXX)		Control Arm (N=XXX)	
Visit		Change from		Change from Change from				Change from
Statistic	Value at Visit	Baseline	Value at Visit	Baseline	Value at Visit	Baseline	Value at Visit	Baseline
Baseline								
n	XXX		XXX		XXX		XXX	
Mean (SD)	xx.xx (xx.xxx)		xx.xx (xx.xxx)		xx.xx (xx.xxx)		xx.xx (xx.xxx)	
Median	XX.XX		XX.XX		XX.XX		XX.XX	
Q1, Q3	xx.xx, xx.xx		xx.xx, xx.xx		xx.xx, xx.xx		xx.xx, xx.xx	
Min, Max	XX.X, XX.X		xx.x, xx.x		xx.x, xx.x		xx.x, xx.x	
< <day x="">></day>								
n	XXX	XXX	XXX	XXX	XXX	XXX	XXX	XXX
Mean (SD)	xx.xx (xx.xxx)	xx.xx (xx.xxx)	xx.xx (xx.xxx)	xx.xx (xx.xxx)	xx.xx (xx.xxx)	xx.xx (xx.xxx)	xx.xx (xx.xxx)	xx.xx (xx.xxx)
Median	XX.XX	XX.XX	XX.XX	XX.XX	XX.XX	XX.XX	XX.XX	XX.XX
Q1, Q3	xx.xx, xx.xx	xx.xx, xx.xx	xx.xx, xx.xx	xx.xx, xx.xx	xx.xx, xx.xx	xx.xx, xx.xx	xx.xx, xx.xx	xx.xx, xx.xx
Min, Max	xx.x, xx.x	xx.x, xx.x	xx.x, xx.x	xx.x, xx.x	xx.x, xx.x	xx.x, xx.x	xx.x, xx.x	xx.x, xx.x
etc.								

N = number of patients in analysis set; n = number of patients with data available.

SD = Standard deviation;Q1 = 25th percentile; Q3 = 75th percentile; Min = Minimum; Max = Maximum.

Notes: The Baseline value is defined as last scheduled or unscheduled non-missing value collected prior to the first dose of the first study drug administration. Reference: Listing 16.2.8.3.2

Programming notes (not part of the table):

- Table template TEG002B.
- Parameter is: Average QTcF interval (msec).

• Visits: Day 1 - Post-infusion, Day 3 - Post-infusion and Day 31.

• The displayed xxx do not reflect actual decimal precision. Please follow Section 2.11 for rounding rules.

xxx (xx.x)

xxx (xx.x)

xxx (xx.x)

xxx (xx.x)

Visit	Plitidepsin 2.5mg	Plitidepsin 1.5mg	Plitidepsin Total	Control Arm	
Parameter	(N=XXX)	(N=XXX)	(N=XXX)	(N=XXX)	
PCI Criterion	n (%)	n (%)	n (%)	n (%)	
< <day x="">> Patients at <<day x="">>, n1</day></day>	XXX	xxx	XXX	xxx	

xxx (xx.x)

xxx (xx.x)

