### Listing 16.2.8.3.1 12-Lead Electrocardiogram (ECG) Parameters (As Treated Population)

Treatment Group: << Plitidepsin 2.5mg/Plitidepsin 1.5mg/Control Arm>>

Site ID - Patient ID	Age/Sex/Race [a]	Parameter (unit)	Visit – Replicate #	Date/Time of Assessment (Day) [b]	Value
XXXX-YYYYY	XX/X/X	XXXXXXXXXX (XXXX)	XXXXXXXXX	DDMMMYYYY /HH:MM (XX)	XXXX
123-456789	45/M/W	PR Interval (msec) QRS Interval (msec) QTcF Interval (msec)	Screening - Replicate 1 Screening - Replicate 2 Screening - Replicate 3 Day 1 - Replicate 1 Day 1 - Replicate 2 Day 1 - Replicate 2 Screening - Replicate 1 Screening - Replicate 2 Screening - Replicate 3 Screening - Replicate 1 Screening - Replicate 1 Screening - Replicate 2 Screening - Replicate 3	19JAN2018/09:25 (-1) 19JAN2018/09:30 (-1) 19JAN2018/09:35 (-1) 20JAN2018/10:05 (1) 20JAN2018/10:10 (1) 20JAN2018/10:15 (1) 19JAN2018/09:25 (-1) 19JAN2018/09:35 (-1) 19JAN2018/09:25 (-1) 19JAN2018/09:25 (-1) 19JAN2018/09:30 (-1) 19JAN2018/09:35 (-1)	228 237 223 223 228 237 99 103 99 393 377 394
etc.			- •		

[a] For sex, F = Female; M = Male. For race, AI = American Indian or Alaska native; A = Asian; BA = Black or African American; PI = Native Hawaiian or Other Pacific Islander; W = White; O = Other; UN = Unknown.

[b] Relative to the start of study treatment.

- Listing template LEG001A.
- Parameters are: heart rate (beats/min); RR interval (msec); PR interval (msec); QRS interval (msec); QT interval (msec); and Fridericia corrected QT (QTcF) interval (msec).
- Include all Visits available in data including any unscheduled Visit.
- The displayed xxx do not reflect actual decimal precision. Please follow Section 2.11 for rounding rules.
- Order by Site ID Patient ID, parameter and Visit.

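### The ECG safety endpoint is declared without limit, but only QTcF is summarised by arm; PR and QRS stay as raw replicate listings

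*SAP*

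**What the plan says.** Section 3.4 lists among the safety variables "Actual and change from Baseline in ECG findings", with no restriction to one interval. The matching objective in section 2.1.3.2 is to compare each plitidepsin dose "versus the control in terms of ECG variations".

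Section 7.7.5 names six quantitative measurements taken in triplicate: heart rate, RR, PR, QRS, QT and QTcF. It then specifies the analysis: "The average QTcF interval (msec) values and changes from baseline will be summarized by treatment group and overall plitidepsin, and by visit". The two criteria for a potentially important result are also QTcF only (average above 500 msec; change above 30 msec).

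The shells follow section 7.7.5:

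- Table 14.3.6.1 is titled "Summary of 12-Lead Electrocardiogram (ECG) Parameters - Change from Baseline (As Treated Population", but its programming notes say "Parameter is: Average QTcF interval (msec" and "Visits: Day 1 - Post-infusion, Day 3 - Post-infusion and Day 31".
- Table 14.3.6.2 tabulates the two QTcF criteria.
- Listing 16.2.8.3.1, "12-Lead Electrocardiogram (ECG) Parameters (As Treated Population", shows all six variables with one row per replicate. It has no column for an average or for a change.
- Listing 16.2.8.3.2 gives averages and changes for QTcF alone.
- Listing 16.2.8.3.3 gives the interpretation and finding text per replicate.

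**The concern.** The endpoint in section 3.4 is stated in terms of actual values and changes from baseline, which are properties of measured quantities. The plan measures six and delivers that endpoint for one. Nothing in section 8 (Changes in Planned Analysis) records a decision to narrow it.

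PR and QRS describe cardiac conduction, which QTcF does not replace. The plan itself treats the heart as an area of interest: section 7.7.2 makes cardiac events adverse events of special interest, including the arrhythmia query and a term for an abnormal QRS complex. If plitidepsin moved mean PR or QRS without producing a reported adverse event, no table in this plan would show it. The ECG-variations objective would then be answered for QTcF only.

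**Working it through.** The plan states no figure to reproduce, so the check sets the declared endpoint against the outputs and then counts what is absent.

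**Step 1. Coverage of each measured variable** (section 7.7.5; Tables 14.3.6.1 and 14.3.6.2; Listings 16.2.8.3.1 and 16.2.8.3.2)

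| Variable | Taken in triplicate | Averaged | Change from baseline | By-arm table |
|---|---|---|---|---|
| QTcF | yes | yes | yes | yes |
| PR, QRS | yes | no | no | no |
| Heart rate, RR, QT | yes | no | no | no |

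One of six variables receives what section 3.4 declares.

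**Step 2. Comparison with the parallel endpoint.** Section 3.4 words the vital-signs endpoint in the same way: "Actual and change from Baseline in vital signs results". Section 7.7.4 names systolic and diastolic pressure, pulse rate, temperature, respiration rate and oxygen saturation. Table 14.3.5.1 summarises all six of these by arm with change from baseline. The same form of endpoint is met for six of six variables there and for one of six here.

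**Step 3. Other places where PR or QRS could appear by arm**

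- Listings 16.2.8.3.1 and 16.2.8.3.3 are grouped by treatment but hold patient-level rows, not a summary.
- The special-interest adverse event tables count reported events. They contain no interval values.
- The QTc substudy has its own analysis plan, not shown here, and covers about 50 patients (section 2.2), not the whole As Treated population.

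**Step 4. Size of the gap for PR and QRS**

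Inputs: 2 intervals; 3 replicates per ECG (section 7.7.5); 4 scheduled ECG visits, namely Screening, Day 1, Day 3 and Day 31 (Appendix 4); 3 post-baseline visits in Table 14.3.6.1.

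- By-arm change summaries absent: 2 x 3 = 6.
- Listed values per patient: 2 x 4 x 3 = 24.
- Triplicate means a reader would have to form per patient: 24 / 3 = 8.
- Changes from baseline a reader would have to form per patient: 2 x 3 = 6.

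The per-patient counts assume complete scheduled ECGs with one triplicate set per visit and no unscheduled recordings.

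**The case against.** The best defence is that this is an open choice of scope. Section 3.4 is generic and names neither PR nor QRS; section 7.7.5 is the operative text, says plainly that QTcF is summarised, and the shells carry it out consistently. Note 4 to the schedule in Appendix 4 describes the ECG visits as an assessment of QTcF prolongation. This stands as a reason for QTcF to lead. It does not narrow the endpoint in section 3.4, nor does it explain a table title that covers ECG parameters in general.

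A second argument is that the phrase used in section 3.4 recurs in the title of Listing 16.2.8.3.3, which holds interpretations, so the endpoint might mean those. That reading fails, because a free-text interpretation has no change from baseline in the sense the endpoint uses.

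A third is that the vital-signs comparison is imperfect: Listing 16.2.8.2.1 also lists FiO2 and PaO2, which Table 14.3.5.1 does not summarise. That is true, and the comparison in Step 2 is therefore limited to the variables named in section 7.7.4, where it holds.

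Two further points carry weight. Choosing PR and QRS from the five untabulated variables is a judgement: the plan identifies no plitidepsin signal in either, and pulse rate already has a by-arm table. The counts in Step 4 also measure missing output, not bias or a changed conclusion. Both keep the point minor; neither supplies the missing summaries.

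**Conclusion.** The concern holds, as a minor point. The plan declares an ECG endpoint in terms of actual value and change from baseline, measures six variables in triplicate, and reports that endpoint by arm for QTcF alone. For PR and QRS, six by-arm change summaries are absent from the As Treated analysis, and the adverse event tables and listings do not stand in for them. No efficacy result, error rate or stopping rule is affected.

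The conclusion rests on reading section 3.4 as not confined to QTcF, which is what its wording supports. It does not depend on what the substudy plan contains, since that plan covers only a subset of patients.

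**What to change.** Add triplicate-mean PR and QRS, actual value and change from baseline, to Table 14.3.6.1 at its three existing visits and under its existing baseline rule, and keep QTcF as the lead parameter. State that the mean is taken over the replicates at each visit, as the average QTcF presumably is. ECG heart rate can be included as a secondary addition.

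The cost is one existing shell run on two more parameters (three with heart rate), all already in the database. If the sponsor does intend QTcF only, the less informative alternative is to restrict the section 3.4 endpoint and the table title to QTcF and give the reason. That removes the inconsistency but leaves PR and QRS unreported by arm.
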